# 6.1. SUBJECT DISPOSITION, DEMOGRAPHIC AND BASELINE CHARACTERISTICS

Subject disposition will be presented for all subjects. The number of subjects who completed the study and discontinued from the study will be provided. The reasons for early discontinuation also will be presented. Additionally, the number of days on study and study medication will be summarized.

Demographic data and baseline characteristics including age, gender, race, ethnicity, and Initial Composite Symptom Score will be summarized using descriptive statistics for the ITT population.

This information will be reviewed for baseline differences, but no statistical testing will be performed.

Subject diary completion will be summarized included the days of diary completion.

#### 6.2. EFFECTIVENESS ANALYSIS

# **6.2.1.** Effectiveness Endpoints

The effectiveness endpoints include:

- Time to resolution of fever
- Time to alleviation of influenza symptoms
- Change in influenza virus titer by TCID50/mL
- Change in RT-PCR results
- Change in virus susceptibility to neuraminidase inhibitors
- Incidence of influenza-related complications
- Usage of antipyretic medication
- Change in daily activities
- Appetite and Eating patterns

# **6.2.2.** Effectiveness Analyses

A subject's oral temperature will be summarized by age group and overall by study visit and treatment group. A subject has Resolution of Fever if he/she has an oral temperature <99.4°F oral or <98.4°F axillary and no antipyretic medications have been taken for at least 12 hours. The time to resolution of fever will be estimated for each age group and overall by treatment group using the method of Kaplan-Meier using temperature and symptom relief medication information obtained from the subject diary data. Subjects who do not have resolution of fever will be censored at the time of their last non-missing post-baseline temperature assessment.

Alleviation of symptoms will be determined by assessment of symptoms as reported on each Subject Diary. The time to alleviation of symptoms will be estimated overall and for individual symptoms for each age group by treatment group using the method of Kaplan-Meier. Subjects who do not experience alleviation of symptoms will be censored at the date of their last non-missing post-baseline assessment.

Change from baseline in  $TCID_{50}/mL$  through Day 3, Day 7 and Day 14 respectively will be presented by age group and overall by treatment group for subjects with positive viral titers at baseline ( $log_{10} \ TCID_{50}/mL > 0.5$ ). A box plot and a histogram of the  $TCID_{50}/mL$  values will be presented by visit, age group, and treatment group. In addition, the median change from baseline in  $TCID_{50}/mL$  will be presented by visit, age group, and treatment group.

The number and percent of subjects with positive viral titers at baseline ( $log_{10} TCID_{50}/mL > 0.5$ ) that are shedding virus at each visit will be presented by age group and overall by treatment group.

The RT-PCR results at each visit will be presented by age group and overall by treatment group for subjects with positive RT-PCR results at baseline.

Change from baseline to last positive value of influenza virus susceptibility to neuraminidase inhibitors will be assessed using virology laboratory tests. Virology laboratory tests will include phenotypic characterizations of influenza virus recovered (hemaglutinin and neuraminidase) and viral susceptibility to zanamivir, oseltamivir, and peramivir, as well as genotyping of virus isolates. These analyses will be presented overall and by age group, treatment group and viral subtype.

The development of any post treatment genotypic changes in neuraminidase and hemagglutinin will be assessed by comparison of sequences from baseline and last positive post-treatment virus samples. These analyses will be presented overall and by age group, treatment group and viral subtype.

The number and percentage of subjects experiencing influenza related complications will be summarized by age group and overall by complication preferred term and treatment group.

The number of doses of antipyretic medications, as recorded in the subject diary, taken throughout the study and by study day will be summarized by age group and overall by treatment group.

The change in daily activities will be summarized each day by treatment group for each age group and overall.

The shift in the assessment of appetite and eating patterns from baseline to each day will be summarized by treatment group for each age group and overall.

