8. SELECTION AND WITHDRAWAL OF SUBJECTS

8.1. Subject Inclusion Criteria

- 1. Male and non-pregnant female subjects age birth to 17 years of age.
- 2. Clinical signs and symptoms consistent with acute influenza infection consisting of an oral temperature ≥ 100°F (37.8°C) or rectal temperature ≥ 101.3°F (≥ 38.5°C) with at least one respiratory symptom (cough or rhinitis) OR a positive influenza rapid antigen test. Fever will either be documented at the time of screening or must be reported by the parent or care-giver if treatment with an antipyretic was given within 6 hours of the screening assessment. Note: enrollment at each site by clinical symptoms alone will be approved by the Sponsor at the beginning of each influenza season once influenza has been confirmed in the local community. The Sponsor may withdraw approval for symptomatic screening in any season based upon trends in influenza surveillance data. Prior to sponsor approval or after approval is withdrawn, criteria 2 must be met by a positive influenza RAT test. During the period of approval, clinical symptoms alone will be adequate to meet criteria 2.
- 3. Onset of symptoms no more than 72 hours before presentation for screening for subjects < 2 years old .
- 4. Written informed consent by parents/guardians and assent by subjects ≥ 7 years of age^{1,2}
- 5. Females who have started their menses must either be:
 - Sexually abstinent
 - Using a highly effective form of birth control such as hormone contraception (oral, patch, injection, implant or vaginal ring) or 2 barrier methods (condom with spermicide and diaphragm)

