# **Alleviation of Symptoms**

A subject has Alleviation of Symptoms if all of the assessed symptoms of influenza assessed on his/her subject diary based on age are either absent or are present at no more than mild severity level and at this status for a 21.5 hour (24 hours -10%) period.

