# Time to Alleviation of Symptoms

Time to Alleviation of Symptoms is the number of hours from initiation of study drug to start of the period in which a subject has Alleviation of Symptoms.

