# 5.2. INTENT-TO-TREAT INFECTED POPULATION

The ITTI population will include all subjects who are enrolled, treated, and have influenza confirmed by RT-PCR. The ITTI population will be used for analyses of effectiveness.

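### Time to alleviation of an individual symptom counts children who did not have that symptom at dosing, because SAP 6.2.2 sets no baseline condition

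*SAP*

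**What the plan says.** **Population.** SAP 5.2: "The ITTI population will be used for analyses of effectiveness". Membership needs enrolment, treatment and a positive RT-PCR, nothing more.

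**Symptoms.** SAP 6.2.2 uses Kaplan-Meier: "The time to alleviation of symptoms will be estimated overall and for individual symptoms for each age group by treatment group". SAP 4.3.8 defines alleviation as every assessed symptom absent or present "at no more than mild severity level and at this status for a 21.5 hour" period. The time is "the number of hours from initiation of study drug to start of the period in which a subject has Alleviation of Symptoms". Neither definition asks for an earlier moderate or severe score, and Protocol 13.8.2 adds no such condition.

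**Fever.** SAP 6.2.2: "A subject has Resolution of Fever if he/she has an oral temperature <99.4°F oral or <98.4°F axillary", with no antipyretic for 12 hours. Fever at the start is not required.

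**Virology, same section.** Change in TCID50 is presented "for subjects with positive viral titers at baseline". Shedding is limited in the same way, and RT-PCR is limited to baseline RT-PCR positives.

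**Entry and baseline.** Protocol 8.1, criterion 2, asks for a raised temperature "with at least one respiratory symptom (cough or rhinitis) OR a positive influenza rapid antigen test". It sets no severity floor for any symptom. In SAP 6.1, "Initial Composite Symptom Score will be summarized using descriptive statistics for the ITT population".

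**Activity and appetite diaries.** Protocol 10.1 stops each item when that item is back to its pre-illness level. Protocol 10.3.3 and 10.3.4 stop at a resolution whose subject is not named, or at final follow-up. Note 10 of Protocol Table 1, repeated in SAP 2.2, stops both when all symptoms have resolved. SAP 6.2.2 tabulates both items by day, SAP 9 counts non-missing values only, and SAP 4.3.4 provides no imputation for them.

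**The concern.** A time-to-recovery analysis should start from children who have something to recover from. The plan applies that principle to virology and leaves it out for the clinical endpoints. Children not at risk enter the Kaplan-Meier curve as events at or near the origin, so the median mixes speed of recovery with the share who had the symptom at dosing.

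Effectiveness against oseltamivir is a secondary objective. With 4:1 allocation, the 7 to <13 and 13 to <18 year cohorts hold about 40/5 = 8 and 30/5 = 6 oseltamivir subjects. In cells that small, a chance difference in who had the symptom can look like a treatment difference.

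**Working it through.** **1. The rule applied to one child.** Sore throat is scored 0 pre-dose and stays 0. The 21.5-hour condition is met, so the event time is the start of that period. This is 0 h if the pre-dose score may open the period, and otherwise the first post-dose reading. The SAP does not say which. It also gives no separate single-symptom definition, so the all-symptom rule is carried over here by reading.

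**2. Inputs.** The documents give no share of children none/mild at dosing, so p is assumed. The recovery median m = 30.5 h (95% CI 22.6 to 45.8) is the all-symptom figure of the Japanese pediatric study (Protocol 5.3.2.1). It is used for a single symptom only as an illustration. Recovery is taken as exponential.

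**3. Continuous time, event at 0 h for those not at risk.** S(t) = (1 − p)·exp(−ln2·t/m), so the median is m·[1 + log2(1 − p)], or 0 if p ≥ 0.5. At p = 0.30: 30.5 × (1 − 0.5146) = 14.8 h.

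**4. Reading grid.** The first reading falls uniformly 0 to 12 h after dosing, then every 12 h. The event is at the first reading at or after recovery, or at the first reading if not at risk (simulated).

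| p not at risk | continuous, h | 12-hourly grid, h |
|---|---|---|
| 0 | 30.5 | 36.6 |
| 20% | 20.7 | 26.8 |
| 30% | 14.8 | 21.0 |
| 40% | 8.0 | 14.2 |
| 50% | 0 | 10.8 |

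**5. Chance imbalance.** Sum the two binomial distributions over all outcomes where the observed shares not at risk differ by at least 20 points. At a true p of 20% the probability is 0.20 for 32 vs 8 subjects and 0.31 for 24 vs 6. At p = 5% it is 0.033 and 0.036. These sizes are enrolment ceilings; the ITTI cells will be no larger. For one symptom, with identical recovery in both arms, 10% vs 30% not at risk would show 25.9 vs 14.8 h in continuous time.

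**6. Overall alleviation.** The event is immediate only if all 5 to 7 assessed symptoms are none or mild at dosing and stay so. If p were 5%, the median would move from 30.5 to 28.2 h.

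**7. Fever.** The same grid is used with the 20.4 h median of that study. With no afebrile entrants the median is 26.6 h. With 10%, 20% and 30% afebrile and no antipyretics it is 23.5, 20.0 and 16.1 h. If every afebrile child takes an antipyretic within 12 h after dosing and the event waits 12 h from it, the figures are 25.7, 25.2 and 24.9 h.

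**8. Appetite by day.** Assume all abnormal on Day 1 and daily recovery h = 20%. On Day 6 the share truly abnormal is 0.8^5 = 33%.
- Protocol 10.1 rule: children still recording number 0.8^4 = 41%, so the table shows 0.33/0.41 = 80% abnormal.
- Note 10 rule: no distortion if symptom clearing is unrelated to appetite. If symptoms clear only after appetite, at 20%, 30% or 50% a day, the table shows 40%, 44% or 51%.

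**The case against.** Several counter-arguments stand, and they limit the point.

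- A reader might infer that the overall alleviation median is seriously distorted. The documents do not support that. Every age-specific list contains feverishness and a respiratory symptom, the children present with acute influenza, and all symptoms must be none or mild at once. Nothing suggests a share of 10 to 20%, so the 20% and 31% imbalance probabilities belong to individual symptoms. At 5% they are about 3 to 4%.
- A reader might infer that fever medians are biased. That needs afebrile entry on a rapid test, and criterion 2's sentence on documenting or reporting fever states no rapid-test exemption. Children whose fever is masked by an antipyretic are at risk and are not part of the problem.
- A reader might take the event time as exactly 0 h. If the pre-dose score cannot open the period, it is the first post-dose reading. The grid figures allow for this.
- The 30.5 h median may itself include children not at risk. If so, applying p counts them twice.
- SAP 10 lists no individual-symptom output. Its main alleviation table carries a footnote mark whose text is not shown, so a condition there cannot be ruled out. None is in the SAP text.
- SAP 6.1 has baseline data reviewed for differences, and symptoms are listed by subject. But a summed score does not show who was at risk for a given symptom.
- A reader might infer that by-day appetite tables will show most children still abnormal. That follows only under the Protocol 10.1 rule; the SAP reproduces note 10. Days 3 and 7 are re-assessed under either rule, as is Day 14 unless done by phone, and n is displayed.

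**Conclusion.** The point holds for individual symptoms. The written rule counts a child without the symptom as an early alleviation, and the resulting median depends on the baseline mix. How far is unknown. On the stated assumptions, 30% not at risk takes 30.5 h to 14.8 h, or 36.6 h to 21.0 h on a 12-hourly grid. Overall alleviation is exposed to the same gap but probably little affected. Fever is affected only under one reading of criterion 2, and by less the more antipyretics are used.

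The diary stop rules are a separate and lesser point. They do conflict. The consequence runs from none to moderate under note 10, and is larger between visits if recording stopped at return to normal.

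No hypothesis is tested, the primary objective is safety, and no error rate is involved. This is worth correcting because the correction is cheap and the oseltamivir cells are small.

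**What to change.** **SAP 6.2.2.**
- Individual symptoms: analyse each in ITTI subjects with that symptom moderate or severe pre-dose. State whether the pre-dose score can open the 21.5-hour period.
- Overall alleviation: add the matching restriction, at least one symptom moderate or severe pre-dose.
- Fever: use ITTI subjects with fever documented at screening, or a pre-dose temperature at or above the route-specific threshold, or caregiver-reported fever after an antipyretic. The screening limb is needed because Protocol 10.1 exempts the baseline reading from the 4-hour antipyretic rule. A child febrile at screening can therefore read below threshold pre-dose.
- Report the numbers not at risk by arm and age group, keep all-ITTI alongside, and list the individual-symptom output in SAP 10.

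**Activity and appetite.** Reconcile Protocol 10.1, 10.3.3, 10.3.4 and note 10 in both documents. For data already collected, add one SAP convention. A last record of normal appetite, or of full ability (10 on the 0 to 10 scale), is carried forward until a later record contradicts it. Alternatively, report Kaplan-Meier time to that state.

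**Cost.** The at-risk sets need SAP text and programming; pre-dose temperature and symptom severity are already collected (Protocol 10.2.2.1). The documents do not show whether caregiver-reported fever is a retrievable field, so that needs checking. The oseltamivir cells shrink: with 30% excluded, 8 × 0.7 = 5.6 and 6 × 0.7 = 4.2, which is why all-ITTI should stay. Rewording the diary rules reaches only remaining enrolment, since the Synopsis reports the older cohorts fully enrolled. For those cohorts the SAP convention is the remedy.

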6.2. Secondary Objectives

- To describe the pharmacokinetics of IV peramivir in pediatric subjects with influenza
- To evaluate the effectiveness of IV peramivir compared to oral oseltamivir in pediatric subjects with influenza
- To evaluate the incidence of influenza complications, specifically otitis media, sinusitis, bronchitis or pneumonia requiring antibiotic use diagnosed after initiation of study drug

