10.2.2.1. Day 1/Baseline/Pre-Dose

The following procedures/evaluations will be performed pre-dose at Baseline on Day 1:

• Body temperature just prior to study drug administration (using the study electronic thermometer via the oral or axillary method).

- Physical examination, including assessment of presence of possible influenza-related complications.
- Vital sign measurements (blood pressure (in children < 2 only if clinically indicated), heart rate, respiration rate).
- Review and recording of concomitant medications.
- Blood specimen collection for clinical chemistry and clinical hematology tests as specified in Sections 11.2.1 and 11.2.2 and a serum sample for future influenza antibody analysis. Subjects whose weight is < 10kg do not require a serum antibody sample.

(Clinical laboratory specimens collected at Screening are for the purpose of establishing a baseline and the results are not required to determine subject eligibility).

- Urine sample collection for routine urinalysis.
- Determination (and recording in the Subject Diary) of the presence and severity of each of the age specific symptoms of influenza (see Section 10.1). Questions asked of subjects age 6 years and older, if possible.
- Determination [with assistance from the subject (if possible)] of the subject's ability to perform usual daily activities.
- Determination [with assistance from the subject (if possible)] of the subject's appetite and eating patterns assessed as either normal or reduced/abnormal.
- Bilateral adequate nasal swab specimen collection for viral subtyping, culture, quantitative PCR assay and susceptibility to neuraminidase inhibitors.
- Administration of the study medication (at Hour 0) and recording of the calendar date and 24-hour clock time for the start and finish of the IV infusion, if applicable. Each subject will receive peramivir, if ≤ 12 then adjusted for body weight, and oseltamivir adjusted for weight in subjects ≤ 12.

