13.9. Safety Analyses

Adverse Events will be mapped to a Medical Dictionary for Regulatory Activities (MedDRA)-preferred term and system organ classification. The occurrence of treatment-emergent AEs (TEAEs) will be summarized by age group and treatment group using MedDRA-preferred terms, system organ classifications, and severity. All AEs will be listed for individual subjects showing both verbatim and preferred terms. Separate summaries of treatment-emergent SAEs and AEs related to study drug will be generated.

Descriptive summaries of vital signs and clinical laboratory results will be presented by age group, treatment group and study visit. Laboratory abnormalities will be graded according to the DAIDS Table for Grading Adverse Events for Adults and Pediatrics (Publish Date: December 2004 Clarification, 2009, see Appendix 1). The number and percentage of subjects experiencing treatment-emergent graded toxicities will be summarized by age group and treatment group. Laboratory toxicity shifts from baseline to post-baseline assessments will be summarized by age group and treatment group.

Previous and concomitant medications will be mapped to a WHO preferred term and drug classification. The number and percent of subjects taking concomitant medications will be summarized using preferred terms and drug classifications.

The number and percent of subjects experiencing influenza related complications will be summarized by age group and treatment group.

Subject disposition will be presented for all subjects. The number of subjects who completed the study and discontinued from the study will be provided. The reasons for early discontinuation also will be presented.

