# 3. OBJECTIVES

The primary objective of the study is to evaluate the safety of IV peramivir compared to oral oseltamivir in pediatric subjects with acute uncomplicated influenza.

The following secondary objectives are planned for this study.

- To describe the pharmacokinetics of IV peramivir in pediatric subjects with influenza.
- To evaluate the effectiveness of IV peramivir compared to oral oseltamivir in pediatric subjects with influenza.
- To evaluate the incidence of influenza complications, specifically otitis media, sinusitis, bronchitis or pneumonia requiring antibiotic use diagnosed after initiation of treatment.

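### The complications objective requires antibiotic use and diagnosis after dosing, but the planned endpoint, analysis and table apply neither condition

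*SAP*

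**What the plan says.** The objective in SAP section 3 is: "To evaluate the incidence of influenza complications, specifically otitis media, sinusitis, bronchitis or pneumonia requiring antibiotic use diagnosed after initiation of treatment". Protocol 6.2 has the same two conditions, ending "pneumonia requiring antibiotic use diagnosed after initiation of study drug", and the protocol synopsis repeats them.

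The endpoint loses both conditions. SAP 6.2.1 lists it as "Incidence of influenza-related complications", and protocol 7.1.2 uses the same label.

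The analysis rule is also unqualified. SAP 6.2.2 says: "The number and percentage of subjects experiencing influenza related complications will be summarized by age group", and goes on to add an overall summary, split by preferred term and treatment arm. Protocol 13.9 says: "The number and percent of subjects experiencing influenza related complications will be summarized by age group and treatment group". The output list in SAP section 10 has one summary of these events, Table 14.2.4, in the intent-to-treat infected (ITTI) population. Its title mentions neither antibiotics nor timing.

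On data collection, protocol 10.2.2.1 includes before dosing: "Physical examination, including assessment of presence of possible influenza-related complications". The visit schedules in protocol 7.3 and SAP 2.2 mark the complications row at the pre-dose baseline as well as at Days 3, 7 and 14 and at early withdrawal. Under protocol 11.4 the investigator notes a complication that the child has or is presumed to have, and any medicine used for it goes on the concomitant-medication page.

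**The concern.** The objective and the analysis define different events. A child with a post-dose complication managed without an antibiotic is outside the objective but inside Table 14.2.4. The SAP does not say how a complication already present before dosing is to be handled.

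If the plan is followed as written, the report will present a figure under this objective that does not estimate it. The trial is open label, so a definition left open can also be settled after the data have been seen.

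**Working it through.** The documents state no rate, power or sample-size figure for this endpoint, so there is nothing to reproduce. The check is mainly a comparison of texts.

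**Step 1: the two conditions, place by place**

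| Place | Antibiotic condition | Onset condition |
|---|---|---|
| Protocol synopsis and 6.2 (objective) | yes | yes |
| SAP 3 (objective) | yes | yes |
| Protocol 7.1.2 (endpoint) | no | no |
| SAP 6.2.1 (endpoint) | no | no; only the word *incidence* |
| Protocol 13.9 (analysis) | no | no |
| SAP 6.2.2 (analysis) | no | no |
| SAP Table 14.2.4 (title) | no | no |

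The restriction to four named complications is not the gap. Protocol 11.4 evaluates the same four, and SAP 6.2.2 breaks the summary down by preferred term.

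**Step 2: whether dropping the conditions can change the count**

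- *Antibiotic use.* Protocol 11.4 records the complication on its own form page and the treatment on another. Recording does not depend on an antibiotic being given, so a complication without one enters the count in SAP 6.2.2 and is outside the objective.
- *Onset.* The checklist is completed before dosing. The SAP defines treatment emergence for adverse events and for laboratory abnormalities (section 4.3.8), but has no such rule for these complications. Counting a baseline case is therefore possible, though no sentence directs it.

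**Step 3: whether another output fills the gap**

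- Protocol 11.1 and 11.4 keep these complications off the adverse event record unless they are serious. The treatment-emergent rule and adverse event tables therefore miss most of them.
- SAP 6.3.2 and Table 14.3.8 summarise concomitant medicines by drug class and generic name, not by the complication treated.
- Listings 16.2.6.8 (complications) and 16.2.4.5 (medications) give subject-level data, but no rule joins them.

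**Step 4: weight of one child**

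Protocol 13.4 plans up to 140 subjects, about 117 on peramivir, so oseltamivir is 140 − 117 = 23. One reclassified child moves an arm's rate by 1/n:

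- peramivir: 1/117 = 0.9 percentage points
- oseltamivir: 1/23 = 4.3 percentage points

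These are planned enrolment figures. Table 14.2.4 uses the ITTI population, which cannot be larger, so the true weights are at least these at the planned split. As a sensitivity case, suppose the oseltamivir children came only from the two cohorts aged 7 or over (40 + 30 = 70) at exactly 4:1. The arm would be 70/5 = 14, and one child would weigh 1/14 = 7.1 points.

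**The case against.** **Incidence implies new onset.** The endpoint label uses that word, and SAP section 3 states the timing condition, so a programmer reading the whole SAP would have grounds to leave out pre-dose findings. This has force on onset. It does not make a rule, and it says nothing about antibiotics.

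**Eligibility removes baseline cases.** Exclusion 10 in protocol 8.2 bars intensive care, organ dysfunction, known or suspected bacterial co-infection, and other viral infections likely to complicate the course. The note beneath it requires influenza to be uncomplicated at entry. Baseline complications should therefore be few. They are not impossible: an otitis, sinusitis or bronchitis judged non-bacterial is not named. The antibiotic gap does not depend on eligibility at all.

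**Stronger readings that the documents do not support.** A reader might infer that the SAP instructs that baseline complications be counted. It does not; this follows only from a missing filter combined with a pre-dose checklist. The documents also do not show that baseline findings go onto the form page behind Table 14.2.4. A reader might also infer that complications without an antibiotic contaminate the result because an antiviral could not affect them. Protocol 5.2.2 points the other way: it reports fewer complications, particularly otitis media, with drugs of this class, and mentions antibiotic use separately. Counting every post-dose complication is a legitimate broader endpoint, but not the one in the objective.

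**The antibiotic phrase may attach to pneumonia alone.** The grammar allows this. Even so, the analysis has no antibiotic condition for pneumonia and no onset condition for any of the four.

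**The study is descriptive.** Protocol 13.3 confirms that nothing is formally tested. That limits the consequence, but a descriptive table should still describe the stated outcome.

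**Conclusion.** The point holds and should be corrected. Followed as written, the plan does not estimate its own secondary objective on complications, and no other planned summary does. The gap is as much the protocol's as the SAP's, because the endpoint in 7.1.2 and the analysis in 13.9 already lack both conditions.

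The antibiotic half is firm. The onset half is a possibility left open, probably affecting few children.

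The size of the discrepancy cannot be calculated, because the documents give neither the rate of complications nor the share treated with antibiotics. A statement that the reported rate would double, or change by any other factor, would have no source. What can be said is that, with about 23 oseltamivir children planned, each reclassified child matters: 4.3 points in that arm against 0.9 in the peramivir arm. Both figures rest on planned numbers.

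**What to change.** In SAP 6.2.2 and Table 14.2.4:

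1. **Main row.** Subjects with at least one of the four named complications that was absent on the baseline checklist, was first diagnosed after the start of study drug, and was treated with an antibiotic on the concomitant-medication record. If the antibiotic condition was meant for pneumonia only, say so.
2. **Linking rule.** State how an antibiotic is matched to a complication: by recorded indication if the form captures it, otherwise by date, with the window given.
3. **Supportive row.** Any complication first diagnosed after dosing, regardless of antibiotic use.
4. **Baseline complications.** List them separately and leave them out of both rows.

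Align protocol 7.1.2 and 13.9 so that objective, endpoint and analysis name the same event.

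No new assessment is needed, since baseline status and treatment of each complication are already required. The cost is a short text change in two documents and a small amount of programming. The documents do not show that an indication or a diagnosis date is captured. If either is missing, a manual review of complications against antibiotic records may be needed, with its rules fixed beforehand.
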